6 ENDPOINTS

6.1 Primary endpoints

The endpoints of the primary objective *To describe medical practices in patients with GCA in terms of patient journey, diagnostic methods and specific GCA treatments since diagnosis* are:

- » Patient journey_(Proportions of each physicians who referred the patient, Proportions of each physicians who followed the patient for his/her GCA, Time between GCA signs/symptoms and diagnosis)
- » Proportions of each diagnostic method used
- » Previous and on-going specific GCA treatments since diagnosis

6.2 Secondary endpoints

The endpoints of the objective *To describe comorbidities related to GCs and associated treatments* are:

- » Comorbidities related to GCs
- » Treatments in patients with comorbidities related to GCs

The endpoints of the objective *To describe GCA characteristics in terms of GCA duration, initial presentation, clinical form and GCA activity*:

- » Proportion of incident patients: patients with a diagnosis of GCA \leq 6 weeks from inclusion
- » Proportion of prevalent patients: patients with a diagnosis of GCA $>$ 6 weeks from inclusion.
- » GCA duration
- » Initial presentation: Proportions of patients with cranial GCA, PMR, extracranial GCA, elevated ESR/CRP and general signs.
- » Clinical form: Proportion of patient with relapse and number of relapse, Distribution of GCs-dependence, Proportions of patients with GCA complications
- » Proportions of each clinical signs/symptoms of GCA activity
- » Score of the physician and patient global arteritis activity VAS

The endpoints of the objective *To describe the health status of GCA patients* are:

- » PRO scores: Total and detailed scores of the SF-36 questionnaire, detailed scores of the EQ5D-3L questionnaire, Total and detailed scores of the FACIT-Fatigue questionnaire

The endpoints of the objective *To describe physician and patient characteristics* are:

- » Demography, medical specialty, number of years of practice, type of practice and number of GCA diagnosis within the previous year for physicians,
- » Demography for patients
- » Significant past and current comorbidities of GCA patients and associated concomitant treatments

7 STATISTICAL METHODS

7.1 Rationale for the number of patients and physicians

7.1.1 *Number of patients required*

Not applicable in a descriptive observational study

7.1.2 *Number of physicians*

Not applicable

7.2 Statistical analyses

The analysis will be performed by ITEC Services in accordance with this section and with the Statistical Analysis Plan (SAP) that supplements it.

7.2.1 *General statistical methods*

The statistical analysis will be performed using SAS® software, version 9.3 or upper.

A SAP describing the planned statistical analysis in detail with Tables, Figures and Listings (TFLs) templates will be developed as a separate document. This SAP will be finalised and validated before each database freeze by CPF.

The descriptive summary statistics will be:

- » for quantitative parameters: mean, standard deviation, median, first and third quartiles, minimum and maximum, filled and missing data;
- » for qualitative parameters: frequency, percentage per modality, filled and missing data

As this is a descriptive study, no statistical testing will be performed. However, 2 sided 95% confidence intervals will be calculated for every relevant proportion / mean.

7.2.2 *Study populations*

Three populations will be defined for the analyses:

- » Population of Physicians: all the specialists who have included at least one patient meeting the eligibility criteria for the study
- » Total Population: all included patients
- » Analysis Population: all included patients meeting the inclusion and non-inclusion criteria

The number of potential exclusions from the patient population used for analysis and the reasons for these exclusions will be described. The patient disposition will be described.

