The index date was defined as the date of first occurrence of GCA code and cases were considered being incident if the GCA code first occurred after a minimal follow-up of 2 years. A treatment sequence was defined as the start of a new drug or the resumption of the same drug after a stop of drug dispensing ≥ 3 months. Annual incidence rates were calculated for the period 2009 to 2015 by using the people recorded in the EGB database as denominator.

Briefly, the results were the following: among the 752,717 patients recorded in the EGB database, 241 people fulfilled inclusion criteria with a mean follow-up of 3.7 (± 2.6) years. Annual incidence was ranging between 7 and 10/100,000 people ≥ 50 years-old that is 2300 patients/year. Demographic analyses showed that 72% of the patients were females and that mean age was 77.5 (± 8.9) years. 74.3% of the patients had at least one proxy (i.e ICD-10 code or a treatment) for hypertension, 39.4% for depression/insomnia and 33.6% for osteoporosis. After index date, temporal artery biopsy (TAB) was performed in 43.2%, high-resolution color Doppler ultrasound in 35.3% and 18FDG-positron emission tomography (PET) in 11.6%.

Regarding treatments, 84.3% of the patients used only GCs while 16.7% also received 1 to 3 adjunctive medications, mainly MTX. Mean 1st GCs sequence duration was 17.2 months (± 16.5) in 96.6% of the patients.

EGB database strengths included comprehensive patient demography, epidemiology, diagnostic methods and treatment sequences. In contrast, limited data were available for comorbidities (as only proxies were described), clinical presentations (cranial, polymyalgia rheumatica [PMR], extracranial), clinical forms (relapsing, GCs-dependant), doses of GCs used, cumulative GCs doses and GCs associated toxicities. In addition, patient journey was poorly described given that patients may be first seen by a variety of physicians according to their first signs and symptoms (e.g. ophthalmologist for blurred vision, neurologist for headache, etc.), data which was not available in the EGB database analysis.

The proportions of use of TAB, Ultrasound or PET have also to be confirmed as they thought to be unusually performed in the EGB analysis.

We propose to conduct an observational study aiming to describe GCA management and patient characteristics in France.

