7.2.3 Analysis of the physician and patient populations

The analyses of the primary and secondary objectives will be performed on the Analysis Population.

7.2.3.1 Analyses of primary objectives:

To describe medical practices in patients with GCA, the following endpoints will be described on the analysis population:

Patient journey

- » Proportions of each physician who referred the patient
- » Proportions of each physician who follows the patient for his/her GCA (internist/rheumatologist)
- » Time between signs/symptoms and diagnosis: described as quantitative variable and as qualitative variable. (early diagnosis / diagnosis in the standard time / late diagnosis)

The 3 endpoints will be described overall and by subgroups: the first 2 endpoints will be described by time between signs/symptoms and diagnosis (qualitative variable) and the 1st and 3rd endpoints will be described by type of physicians who follows the patient.

Diagnostic mean

- » Proportions of each diagnostic method used

The diagnostic mean will be described overall, by time between signs/symptoms and diagnosis (qualitative variable), and by type of physicians who follows the patient.

Previous and on-going specific GCA treatments since diagnosis

- » Previous and on-going specific GCA treatments since diagnosis

Treatments will be coded using the WHO Drug medicine dictionary (ATC codes). They will be described overall and by type of physician who follows the patient.

7.2.3.2 *Analyses of secondary objectives*

The analysis of the secondary objectives will be performed on the analysis population.

Description of comorbidities related to GCs and associated treatments

- » Current and past comorbidities of GCA patients (comorbidities related to GCs) will be coded using the medical dictionary MedDRA®. They will be described overall and by type of physicians who follows the patient.
- » Treatments in patients with comorbidities related to GCs will be coded using the WHO Drug medicine dictionary (ATC codes). They will be described overall and by type of physician who follows the patient.

Description of GCA characteristics

- » Time between diagnosis and inclusion will be described as quantitative variable and as qualitative variable (patient newly diagnosed or not: incident or prevalent case)
- » Proportion of incident patients: patients with a diagnosis of GCA \leq 6 weeks from inclusion
- » Proportion of prevalent patients: patients with a diagnosis of GCA $>$ 6 weeks from inclusion.

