5.1 Descriptive statistics

Each modality of qualitative data will be presented with their number and percentage.

For quantitative data, mean, median, minimum and maximum as well as standard deviation and interquartile range will be described.

For all the variables, number of available and missing observations will be specified. If necessary, 95 % CI will also be presented.

Data will be presented using an appropriate number of decimal places (i.e. the number of decimal places used does not imply undue precision):

- Raw data : same number of decimal as collected,
- Derived data: The appropriate number of decimal places will be determined by general practice, mathematical rationale or scientific rationale (e.g. age should be presented in whole numbers),
- Mean, median and standard deviation : reported to one decimal place greater than the raw/derived data that they summarise,
- Minimum and maximum : same precision as the raw data,
- Percentage : one decimal place,
- P-values : four decimal places (e.g.: $p=0.0037$), after rounding. P-values which are less than 0.0001 will be presented as '<0.0001'.

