- GCA activity

- Scores of the physician global arteritis activity VAS will be analysed as quantitative variables and in classes (≤ 50 ; > 50 mm).
- Scores of the patient global arteritis activity VAS will be analysed as quantitative variables and in classes (≤ 50 ; > 50 mm).

The VAS scores of physician and patient will be divided into classes. The same cut-off (≤ 50 ; > 50 mm) for the two scores will be defined by CHUGAI according to their medical relevance.

In this case, the concordance between the scores of the patient and physician global arteritis activity VAS will be evaluated using the kappa K coefficient, which will be interpreted as follows:

- $K < 0.0$: No match
- $0.0 \leq K \leq 0.2$: Poor agreement
- $0.2 < K \leq 0.4$: Fair agreement
- $0.4 < K \leq 0.6$: Moderate agreement
- $0.6 < K \leq 0.8$: Good agreement
- $K > 0.8$: Very good agreement

To evaluate the GCA activity, the score of the physician global arteritis activity VAS will be used. For this score a threshold value = 10 mm was defined and validated by CHUGAI.

Patients with physician's VAS score less than or equal to 10 mm will be considered with "non-active GCA", while patients with physician's VAS score greater than 10 mm will be considered with "active GCA".

In this case, the potential associated factors with the increase of the GCA activity will be studied by logistic regression.

The outcome variable will be GCA (active/ Non-active). First, a univariate analysis will be conducted. All significant factor at the 20% threshold will be selected for a multivariate analysis. A backward elimination procedure will be used with a threshold of 5%.

The associated factors that will be studied are:

- Age (in classes)
- Gender (Male/Female)
- BMI at diagnosis (in classes)
- Smoking status (Smoker/ Former smoker/ never smoker/unknown)
- Prevalent or incident patient,
- Physician who referred the patient,
- Patient considered with late diagnosis by the physician who referred him (Yes/ No)
- Patient with at least one cranial GCA symptom at diagnosis (Yes/No),
- Patients with at least one PMR symptom at diagnosis (Yes/No),
- Patient with at least one extracranial GCA symptom at diagnosis (Yes/No),
- Patient with abnormal value of ESR (ESR>50 mm/h) at diagnosis
- Patient with abnormal value of CRP (CRP> 25 mg/L) at diagnosis (Yes/No),
- Patient with fever at diagnosis (Yes/No),
- Patient with weight loss at diagnosis (Yes/No),

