5.6 Changes from protocol

Current and past treatments used for comorbidities related to GCs will not be described as mentioned in the protocol regarding to the modifications of the CRF from version 1.2 to version 3.0 according to sponsor's decision. Indeed the dedicated table for specific treatments for comorbidities related to GCs was deleted.

This listing will include all treatments taken by patients with comorbidities related/aggravated by the use of glucocorticoids according to investigator's judgment.

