Table 5 - Efficacy analysis – Diagnostic elements used for GCA diagnosis – Analysis population (N=XX)

Parameter	Statistics	Total (N=XX)
No Intermediate	n(%) n(%) Filled, n(%) Missing, n(%)	
18FDG positron emission tomography (PET) done Yes No	n(%) n(%) Filled, n(%) Missing, n(%)	
If Yes, contributing to the diagnosis Yes No Intermediate	n(%) n(%) n(%) Filled, n(%) Missing, n(%)	
Aortic angiography by CT (angio-CT) done Yes No	n(%) n(%) Filled, n(%) Missing, n(%)	
If Yes, contributing to the diagnosis Yes No Intermediate	n(%) n(%) n(%) Filled, n(%) Missing, n(%)	
Magnetic resonance angiography done Yes No	n(%) n(%) Filled, n(%) Missing, n(%)	
If Yes, contributing to the diagnosis Yes No Intermediate	n(%) n(%) n(%) Filled, n(%) Missing, n(%)	
Other diagnostic method Yes No Intermediate	n(%) n(%) n(%) Filled, n(%) Missing, n(%)	

The percentages are calculated compared to filled data
STUDY : CHUGAI-ARTEMIS - Edition date: DDMMYY
Pgm : EFFICACYJOURN.SAS

The same table will be presented by type of diagnosis (Early /in standard time/late) and by type of physicians who follows the patient.

Listing 2 : Other diagnostic elements used for GCA diagnosis (N= XX)

Patient ID	Newly /not newly diagnosed patient	Type of diagnosis	Physician who follows the patient	Date of used diagnostic element	Other diagnostic element	Contribution to the diagnosis

STUDY : CHUGAI-ARTEMIS - Edition date: DDMMYY
Pgm : EFFICACYJOURN.SAS

Table 6 - Efficacy analysis – Immunosuppressants for GCA taken since diagnosis and stopped before inclusion – Analysis population (N=XX)

Parameter	Statistics	Total (N=XX)
Patient has taken at least one immunosuppressants since diagnosis and stopped before inclusion		
No	n(%)	
Yes	n(%)	
	Filled, n(%)	
	Missing, n(%)	
IF YES		
Used immunosuppressants		
Azathioprine	n(%)	
Cyclophosphamide	n(%)	
Cyclosporine	n(%)	
Leflunomide	n(%)	
Methotrexate	n(%)	
Mycophenolate Mofetil	n(%)	
Other	n(%)	
IF Azathioprine		
Duration of treatment (months)	Mean	
	SD	
	Median	
	[Q1 ; Q3]	
	[Min ; Max]	

Table 6 - Efficacy analysis – Immunosuppressants for GCA taken since diagnosis and stopped before inclusion – Analysis population (N=XX)

Parameter	Statistics	Total (N=XX)
	Filled, n(%) Missing, n(%)	
If Cyclophosphamide		
Duration of treatment (months)	Mean SD Median [Q1 ; Q3] [Min ; Max] Filled, n(%) Missing, n(%)	
If Cyclosporine		
Duration of treatment (months)	Mean SD Median [Q1 ; Q3] [Min ; Max] Filled, n(%) Missing, n(%)	

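### Promised 95% CIs are absent from every primary table shell, and the by-physician-type split from the treatment tables; neither change is declared, and no CI method or allowance for physician clustering is given

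*Protocol*

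**What the plan says.** **Intervals.** Protocol 7.2.1, repeated in the synopsis, rules out testing and then commits to intervals: "However, 2 sided 95% confidence intervals will be calculated for every relevant proportion / mean". SAP 5.1 has instead: "If necessary, 95 % CI will also be presented". It names neither endpoints nor a method. Tables 2-11 provide for counts, percentages, mean, SD, median, quartiles, range, filled and missing. The only intervals in the 35 shells belong to the odds ratios in Tables 22, 23, 26 and 27, all secondary.

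**Split by physician type.** For specific GCA treatments, Protocol 7.2.3.1 says: "They will be described overall and by type of physician who follows the patient". The SAP honours this kind of promise for diagnostic tests, with a note after Table 5: "The same table will be presented by type of diagnosis (Early /in standard time/late) and by type of physicians who follows the patient". No such statement appears in SAP 5.4 for treatments other than glucocorticoids, or with Tables 6-11. Glucocorticoid use is handled in SAP 5.5.2, where the split is kept.

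**Declared changes.** SAP 5.6 lists one change, on another matter: "Current and past treatments used for comorbidities related to GCs will not be described as mentioned in the protocol".

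**Grouping.** The plan is for 300 patients through 150 active physicians, with at most 10 patients per hospital department (Protocol 4.1). Neither document mentions clustered, robust or mixed-model variance.

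**Following physician.** The internist/rheumatologist proportion is a primary endpoint. Only internists and rheumatologists are recruited (Protocol 3.4.1).

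**The concern.** The protocol gives no sample-size or precision rationale (section 7.1) and plans no tests, so intervals are the only planned statement of precision for the primary objective. One stated reason for the study is to check figures from the earlier claims-database (EGB) analysis: "The proportions of use of TAB, Ultrasound or PET have also to be confirmed". If the shells are programmed as drawn, these proportions will be reported without an interval, and non-glucocorticoid treatments without the promised comparison of internists and rheumatologists.

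If intervals are added later by default, they will probably treat patients as independent. Referral, test choice and drug choice are practices, and patients of one physician may resemble each other on them. The activity outcome is itself the physician's rating: "To evaluate the GCA activity, the score of the physician global arteritis activity VAS will be used".

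The following-physician share raises a separate issue. Patients enter only through recruited specialists, so the share is driven largely by who took part and how many patients each included. Printed without comment, it could be read as a finding about French care.

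**Working it through.** There is no stated precision figure to reproduce.

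**Inputs.** N = 300 patients and a target of 150 physicians, so 300/150 = 2 each (Protocol 3.4.3, 3.5.1). EGB proportions: temporal artery biopsy 43.2% and PET 11.6%, in 241 people (Protocol 1). The within-physician correlation ρ is not given; 0.05 to 0.3 is assumed.

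**Formulas.** Design effect DE = 1 + (m − 1)ρ, with m = Σmᵢ²/Σmᵢ. Half-width = 1.96·√(p(1 − p)·DE/300). Coverage of an independence interval = 2Φ(1.96/√DE) − 1.

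**Independence.**
- Biopsy: 1.96·√(0.432·0.568/300) = 5.6 points.
- PET: 1.96·√(0.116·0.884/300) = 3.6 points.

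**Two patients per physician.** DE = 1.05 to 1.30.
- Biopsy: 5.6·√DE = 5.7 to 6.4 points.
- PET: 3.7 to 4.1 points.
- Coverage: 94.4% to 91.4%.

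**Uneven inclusion (illustrations only; the actual distribution is unknown).**
- 50 physicians with 4 patients and 100 with 1: m = (50·16 + 100·1)/300 = 3, DE = 1.1 to 1.6, biopsy ±5.9 to ±7.1, coverage 93.8% to 87.9%.
- 16 physicians with 10, one with 7 and 133 with 1: m = (1600 + 49 + 133)/300 = 5.94, DE = 1.25 to 2.48, biopsy ±6.3 to ±8.8, coverage 92.1% to 78.7%. This is the most uneven split with 1 to 10 patients each. It also needs the single-digit order number in the patient code to include 0.

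**Logistic models.** Variance inflation is about 1 + (m − 1)·ρx·ρy, for factor and outcome correlations ρx and ρy. At m = 2:
- A factor that does not cluster is unaffected.
- With 0.2 and 0.2, inflation is 1.04; the 5% and 20% thresholds act as 5.5% and 20.9%.
- With 0.5 and 0.3, inflation is 1.15; they act as 6.8% and 23.2%.

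**Sparse drug rows.** The EGB report says "16.7% also received 1 to 3 adjunctive medications, mainly MTX". Applied to 300 patients that is about 50, over 15 named drugs, so rows with very few patients are likely. At 0/300 a Wald interval has zero width; Clopper-Pearson runs from 0 to 1 − 0.025^(1/300) = 1.2%. This is a rough guide: the two EGB percentages (84.3% and 16.7%) add to 101%, and its data end in 2015, before tocilizumab's 2017 authorisation.

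**Following-physician share.** With 2 patients each, 60 rheumatologists of 150 give 120/300 = 40%, and 90 give 180/300 = 60%. With 75 of each specialty, 3 patients per internist and 1 per rheumatologist give an internist share of 225/300 = 75%; the reverse gives 25%.

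**Comparison with EGB.** EGB's own half-width at 43.2% is 1.96·√(0.432·0.568/241) = 6.3 points. For the difference between the sources, √(5.6² + 6.3²) ≈ 8.4 points under independence.

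**The case against.** **Intervals have not been withdrawn.** The protocol limits its promise to relevant estimates and SAP 5.1 keeps intervals available, so both leave discretion. That stands: a reader might infer that intervals were cancelled, and the SAP does not say so. But the protocol assigns the table templates to the SAP, and if the primary proportions are not relevant it is hard to say what is.

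**A reader can compute an interval from n and the filled count.** True for an independence interval, but not for one that allows for physicians.

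**An interval in Table 5 would not settle the EGB question.** This stands. EGB has its own sampling error and counted tests after the index date, while SAP 5.4 counts only tests from the month before to the month after diagnosis.

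**Clustering is minor.** At the planned average it is. Coverage near 79% needs both the highest assumed correlation and extreme imbalance. Nor should poor Wald coverage for rare drugs be blamed on clustering: at a true 1% it is 79.9% with independent data and 76% to 79% with clustering, and neither document names Wald. In the logistic models the shift is small beside the effect of screening 22 candidate factors for relapse and then eliminating backward.

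**Selection is already checked, and no national claim is made.** Protocol 3.4.2 plans a comparison of physician characteristics with national data, and 9.1.2 a comparison with the source list. No text says the share estimates who follows GCA patients in France, so that stronger reading fails. What remains is that 9.1.2 compares patients with active physicians only by geography and facility. Listing 1 describes other following physicians with investigator fields, which suggests the variable is the investigator's specialty, but the revised CRF is not available to confirm it.

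**Conclusion.** The point holds as a mismatch between protocol and SAP that should be corrected. Following the SAP as drawn gives primary results without the promised intervals, and non-glucocorticoid treatments without the promised split, with neither change recorded. This part rests on the text alone.

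The clustering part is real but modest. Independence intervals at two patients per physician would be about 2% to 14% too narrow in half-width terms (√1.05 to √1.30), and more so if inclusion is uneven. It rests on an assumed correlation of 0.05 to 0.3 and on the 150-physician target being met. The documents do not support reading it as a threat to the study or to the exploratory models. The following-physician share needs a caveat, not removal from the primary endpoints.

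**What to change.** 1. In SAP 5.1, replace the conditional sentence with a commitment to 95% intervals for the primary proportions (referring physician, diagnosis-delay class, each diagnostic test, each treatment class and drug) and for mean time to diagnosis. Use variance clustered by investigator number, for example SURVEYFREQ and SURVEYMEANS, with Wilson or Clopper-Pearson type limits, and the ordinary Clopper-Pearson interval for zero counts. Add the rows to the relevant shells among Tables 2-11. Table 2 shows time to diagnosis only in classes, so the quantitative row that SAP 5.4 calls for must be added too. State a minimum number of patients and physicians below which per-drug durations and doses get no interval.
2. Add the by-physician-type version of Tables 6-11, at least for the proportions.
3. Keep the following-physician share as an endpoint, with a footnote that it reflects the specialists recruited and a cross-reference to Table 32.
4. Record in SAP 5.6 any protocol interval or split that will not be produced.
5. Where results are set beside EGB, state its sampling error and its different test window.

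Optional: cluster-robust variance by investigator for the final logistic models.

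**Cost.** SAP wording, table rows and some programming. No new data are needed, because the investigator number is the first three digits of the patient number (Protocol 5.3). Intervals become slightly wider. Correlation between physicians of one department would still not be captured.
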